Weight change and the risk of chronic pain following hip and knee arthroplasties: A nationwide registry-based cohort survey study.

Authors/Collaborators:

[name]^{1,2,3}, MD, PhD Fellow; [name]^{1,3}, MD, PhD Fellow; [name], PhD, Associate professor⁴; [name], DMSc, Professor^{1,3}

Affiliations:

1. Department of Orthopaedic Surgery and Traumatology, Copenhagen University Hospital, Bispebjerg and Frederiksberg, Copenhagen, Denmark; 2. The Parker Institute, Copenhagen University Hospital, Bispebjerg and Frederiksberg, Copenhagen, Denmark; 3. University of Copenhagen, Department of Clinical Medicine, Faculty of Health and Medical Sciences; 4. Department of Orthopaedic Surgery and Traumatology, Odense Hospital, Odense, Denmark.

INTRODUCTION

The treatment of hip and knee osteoarthritis not responding to non-surgical treatments may be surgical joint arthroplasty.¹ Though arthroplasty is considered an effective and safe treatment, unfavourable outcomes have been reported,² including persistent postoperative pain (PPP). The association between body weight and outcomes following total hip arthroplasty (THA) and knee arthroplasty is well documented: overweight carries higher risk of bad functional and surgical outcomes.³⁻⁹ Also, Preoperative weight reduction reduces general health related complications following knee arthroplasty.¹⁰ However, only few studies have investigated weight change following THA and knee arthroplasty.¹¹⁻¹⁶ Of these, some have indicated that weight change influences postsurgical outcomes.

Identification of factors that are linked to the incidence of PPP could help us to prevent this problematic outcome. The objective of this study is to investigate whether weight change is associated with the incidence of PPP following THA and knee arthroplasty across non-obese and obese patients.

METHODS

Study design

The study is a nationwide, register-based cohort survey study. We will report the results following the CROSS checklist for standardized reporting of survey studies.¹⁷ We will investigate the change of BMI 11-15 months after THA and knee arthroplasty and incidence of PPP by combining data from national registries and surveys.

Questionnaire

A 22-question questionnaire will be sent to the eligible candidates (see NCT05900791 and NCT05845177). The questionnaire is developed by combining domains from previously validated Patient Reported Outcome Measures (PROMs). Five questions are taken from the Western Ontario and McMaster Universities Osteoarthritis Index (WOMAC) pain domain; seven questions from the Douleur Neuropathique 4 interview (DN4i); a numerical rating scale (NRS) question for pain in the operated joint in the last week; satisfaction; a single question for each of the following: willingness to repeat the surgery; pain frequency; pain interference with daily activities; other chronic pain conditions; patient-reported use of analgesics; weight; height and the permission to contact respondents again later. Patient reported weight and height has been recently found valid in a Danish e-survey setting.¹⁸ A detailed description of the questionnaires and the current validation status of the domains can be found in 2 different papers.^{19,20} The Danish and an English version of the questionnaire will be available in the final publication.

Sample characteristics

Patients with THA and knee arthroplasty who received their arthroplasty 11-15 months prior to the intended date of survey administration will be identified based on the NOMESCO (Nordic Medico-Statistical Committee) Classification of Surgical Procedures from the the Danish National Patient Register by using SKS-code. The codes for THA patients will be SKS-code DM16 [hip osteoarthritis] + KNFB20 or KNFB30 or KNFB40[Primary Total Hip Arthroplasty]. For total knee arthroplasty (TKA), SKS-code DM17 [knee osteoarthritis] + KNGB20, KNGB30 or KNGB40 [primary total knee arthroplasty]). For medial unicompartmental knee arthroplasty (UKA), SKS-code DM17 [knee osteoarthritis] + KNGB01 or KNGB11 [primary medial unicompartmental knee arthroplasty]. The baseline characteristics of the sample including their BMI will be gathered from the Danish Hip Arthroplasty Register (DHR) and the Danish Knee Arthroplasty Register (DKR).

Survey administration

The data of this study is pooled from 2 surveys sent to THA and knee arthroplasty patients.^{19,20} Both surveys are distributed via 'Digital Post' which is linked to the unique Civil Registration number (CPR) using Research Electronic Data Capture (REDCap) software (www.r-project.org). A reminder will be sent 14 days after distribution for non-responders. A month after distribution date, a text-message will be sent to non-responder's telephone number if it is registered in the electronic patient file.

Statistical analysis

We expect to find a sample of around 6400 patients divided between hip and knee arthroplasty. Estimated response rates of 70% will leave us with 2240 patients to be analysed in each joint arthroplasty group. With an expected 15% of the sample to be weight gainers, we will be able to detect a minimum of 16.6% difference in the incidence of the outcome between gainers and non-gainers with a significance level of 0.05 with a power of 0.80.

We will report results for THA, TKA and medial UKA separately as we believe these are different patient groups. We will categorize patients into weight gainers ($\geq 5\%$ weight gain after arthroplasty), weight losers ($\geq 5\%$ weight loss) and those who maintain their weight. Descriptive statistics of the baseline characteristics of the three categories with the following variables will be presented in table 1: age, sex, BMI and surgical details (type of anaesthesia, operation length, use of local infiltration analgesia (LIA), use of cement, and surgical complications).

The primary outcome is the occurrence of PPP and will be defined as NRS pain score higher than 3 as proposed by Moore et. al.²¹ Secondary outcomes include satisfaction defined as being very satisfied or

satisfied; willingness to repeat the surgery defined as answering “yes” in willingness question; frequent pain defined as experiencing pain constantly, daily or few times a week; use of analgesic; interference with daily activities, defined as answering “some”, “much” and “very much”; WOMAC pain score will be reported as the mean (standard deviation [SD]). Following outcome dichotomization (except for WOMAC pain), we will employ a multivariate logistic regression model to estimate the Odds Ratio (OR) and the corresponding 95% Confidence Interval (CI) amongst gainers and losers in relation to those who maintained their weight. For WOMAC pain, we will report the mean difference (MD) and the corresponding 95% CI. We will stratify for baseline obesity status (non-obese: $BMI < 30 \text{ kg/m}^2$, Obese: $BMI \geq 30 \text{ kg/m}^2$). We will run a non-adjusted analysis first, then we will adjust for age, sex and the use of cement. We will do a sensitivity analysis to see whether the effect size is different between non-morbidly obese ($BMI 30-39 \text{ kg/m}^2$) and morbidly obese ($BMI \geq 40 \text{ kg/m}^2$), we will run another sensitivity analysis adjusting for patients having other chronic pain condition. Data is handled in the most recent version of R (www.r-project.org).

Table 1 (Demographics)

	THA			TKA			Medial UKA		
Demographics	Weight gainers	Weight losers	Weight unchanged	Weight gainers	Weight losers	Weight unchanged	Weight gainers	Weight losers	Weight unchanged
Total N									
Age (mean)									
Female N (%)									
BMI (mean)									
General Anaesthesia N (%)									
Spinal Anaesthesia N (%)									
Operation time (mean)									

Use of Cement N (%)									
Local Infiltration of analgesia N (%)									
Surgical complication N (%)									

Table 2 (Risk of developing PPP)

	Weight unchanged (Reference group)				Weight gainers					Weight losers				
	N	PPP: N (%)	OR (95% CI)	P value	N	PPP: N (%)	OR (95% CI)	Adjusted OR (95% CI)	P value	N	PPP: N (%)	OR (95% CI)	Adjusted OR (95% CI)	P value
THA														
Non-Obese			1											
Obese			1											
TKA														
Non-Obese			1											
Obese			1											
Medial UKA														
Non-Obese			1											
Obese			1											

HEALTH RESEARCH ETHICS AND GENERAL CONSIDERATIONS

Funding

Section for Biostatistics and Evidence-Based Research, the Parker Institute, Bispebjerg and Frederiksberg Hospital is supported by a core grant from the Oak Foundation (OCAY-18-774-OFIL), which had no role in study design or writing of this protocol.

Patient and Public Involvement (PPI)

This project follows the EULAR recommendations for the inclusion of patient representatives in the contemporary scientific process.²² A panel of patients helped in developing the questionnaire.

Conflict of interest

All will be disclosed.

Disclaimers

The views expressed in the submitted protocol are the authors' own and not an official position of the institution or funder.

Ethics

The local institutional review board approved the study, and the Danish Health Data Authority will provide contact information for potential respondents. Telephone numbers for non-respondents are found by searching the CPR number in the electronic patient files, but without accessing the patients' health data. According to Danish legislation, approval from the national ethics committee is neither required nor possible to obtain for survey studies.

Because we will link survey responses with perioperative data from the Danish Knee Arthroplasty Register, responses are not anonymous. However, only the authors will have access to confidential information and data will be anonymised as soon as possible. Until then, the data are stored pseudonymised at a logged and encrypted drive.

REFERENCES

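### The 80% power statement describes an undivided joint group comparing gainers with all non-gainers, whereas the plan reports gainers against weight-unchanged patients within procedure-by-obesity strata

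*Combined protocol and SAP*

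**What the plan says.** The planning paragraph of the Statistical analysis section starts from the total: "We expect to find a sample of around 6400 patients divided between hip and knee arthroplasty". It continues: "Estimated response rates of 70% will leave us with 2240 patients to be analysed in each joint arthroplasty group". The share of gainers is given as "With an expected 15% of the sample to be weight gainers", and the conclusion is that "we will be able to detect a minimum of 16.6% difference in the incidence of the outcome between gainers and non-gainers". The test level is 5% and the power 80%.

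The analysis set out in the same section differs in three ways:

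- **Procedure.** "We will report results for THA, TKA and medial UKA separately as we believe these are different patient groups". The 2240 knees are therefore divided into TKA and medial UKA.
- **Obesity.** "We will stratify for baseline obesity status", with the cut at BMI 30. Table 2 prints the reference OR of 1 only on the Non-Obese and Obese lines under each procedure.
- **Comparator.** Odds ratios for gainers and for losers are both taken against patients whose weight was unchanged, so losers are not in the reference group.

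No power or precision figure is given for any stratum or for medial UKA.

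**The concern.** A power statement is useful only if it describes an estimate that the study will report. Here the population (a whole joint group) and the contrast (gainers v everyone else) both differ from what Table 2 contains. The Introduction frames the objective across non-obese and obese patients, so the strata carry the main results and are not a side analysis.

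What is at stake is how null results are read. Someone who sees an inconclusive OR for obese medial UKA, and who has read the planning paragraph, may credit it with 80% power that was never calculated for that row.

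**Working it through.** **Inputs from the documents.** 6400 patients, 70% response, two joint groups, 15% gainers, alpha 0.05, power 0.80. Sidedness is not stated; two-sided is used because it reproduces the plan's figure.

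**Reproducing the plan.**

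- 6400 x 0.70 / 2 = 2240. Gainers: 0.15 x 2240 = 336. Non-gainers: 1904.
- Detectable h = (1.960 + 0.842) x sqrt(1/336 + 1/1904) = 2.802 x 0.0592 = 0.1658, which rounds to 0.166.
- A one-sided test gives 0.147 and pooling both joints gives 0.117, so neither matches.
- As percentage points the figure does not reproduce. For 336 v 1904, 80% power is reached at 5.4, 6.9, 7.8 and 8.3 points for comparator incidences of 10, 20, 30 and 50%.

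The 16.6% is therefore an arcsine effect size for the undivided joint group, with losers in the comparator.

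**Assumptions not in the documents.** UKA 15-25% of knees, obese 30-45%, losers 15-25%, gainers 15% in every row (so 60-70% weight unchanged), 20% PPP in the reference group, no covariate adjustment.

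**Formulas.** Row size = 2240 x procedure share x obesity share. With s = sqrt(1/n1 + 1/n0), where n1 is gainers and n0 is weight unchanged:

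- Power for h = 0.166 is Phi(0.166/s - 1.960).
- The detectable difference d solves d = 1.960 x sqrt(pbar(1 - pbar)) x s + 0.842 x sqrt(p1(1 - p1)/n1 + p0(1 - p0)/n0), where p1 = p0 + d and pbar is the pooled proportion.

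**Two examples, each at its least favourable shares.**

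- THA obese: 2240 x 0.30 = 672; 100.8 gainers v 403.2 unchanged; s = 0.1114; Phi(1.491 - 1.960) = 0.32; d = 13.4 points.
- Medial UKA obese: 2240 x 0.15 x 0.30 = 100.8; 15.1 v 60.5; s = 0.2875; Phi(0.577 - 1.960) = 0.08; d = 36.7 points.

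**All rows, over the assumed ranges.**

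| Table 2 row | Patients | Gainers | Power for h = 0.166 | Detectable points at 20% | Power for 16.6 points at 20% |
|---|---|---|---|---|---|
| Planned: 336 v 1904 | 2240 | 336 | 0.80 | 6.9 | >0.999 |
| THA non-obese | 1232-1568 | 185-235 | 0.52-0.64 | 8.5-9.8 | 0.995-0.999 |
| THA obese | 672-1008 | 101-151 | 0.32-0.46 | 10.7-13.4 | 0.92-0.99 |
| TKA non-obese | 924-1333 | 139-200 | 0.42-0.57 | 9.2-11.4 | 0.98-0.997 |
| TKA obese | 504-857 | 76-129 | 0.25-0.40 | 11.6-15.7 | 0.84-0.97 |
| Medial UKA non-obese | 185-392 | 28-59 | 0.12-0.21 | 17.6-26.7 | 0.46-0.76 |
| Medial UKA obese | 101-252 | 15-38 | 0.08-0.15 | 22.2-36.7 | about 0.3-0.59 |

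**Where the loss comes from.** Dropping losers alone, in an undivided group of 2240, leaves 336 v 1344-1568. The detectable difference moves from 6.9 to 7.0-7.1 points and power for h = 0.166 from 0.80 to 0.78-0.79. The splits do the rest. For example, with UKA at 20% of knees and 20% losers, medial UKA undivided (67 v 291) detects 16.5 points; its obese part at 40% obesity (27 v 116) detects 26.8.

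**The case against.** The strongest reply takes the plan at its word: "detect a minimum of 16.6% difference in the incidence of the outcome between gainers and non-gainers" reads as percentage points. At 20% incidence every THA and TKA row then keeps power of 0.84 or more for 16.6 points, so four of the six rows meet the stated power. This stands. A reader might infer from the mismatch that no row has 80% power for the stated difference; the documents do not support that. What they show is that the calculation was not made for these rows.

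Three further limits also stand:

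- The shortfall in medial UKA on the percentage-point reading depends on the incidence, which the documents do not give. At 10%, non-obese medial UKA detects 14.3 points under the most favourable shares and so reaches 80% power for 16.6. At 30%, obese TKA can need up to 17.2 points and so miss it.
- Nothing in the text presents 16.6% as a relative difference, so no conclusion should rest on that reading.
- The procedure lines in Table 2 carry no reference OR and look like headings, but the table was read from PDF. If the THA line is a result row, it would hold the planned 2240, still with weight-unchanged patients as comparator. The combined knee group is absent on either reading.

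It can also be said that a survey of all eligible patients will recruit no differently whatever the power paragraph says. That is true, but it makes this a point of wording and interpretation; it does not remove it.

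**Conclusion.** The point holds. That the power statement and the reported analyses refer to different populations and different contrasts follows from the documents alone. The size of the consequence rests on the assumed UKA, obese and loser shares, 15% gainers in every row and, for differences in points, a 20% reference incidence.

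For the effect that the numbers actually planned for (h = 0.166), all six rows are below 80% power under these assumptions. For a literal 16.6 points at 20% incidence, only the two medial UKA rows are. The obesity split and the TKA/UKA split cause nearly all of the loss; the change of comparator matters for consistency but costs little power.

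**What to change.** Rewrite the planning paragraph for the analyses that will be reported. For each Table 2 row (THA, TKA and medial UKA, non-obese and obese), give the expected numbers of gainers and weight-unchanged patients and one detectable difference between them, in percentage points or as an OR at a stated reference PPP rate. State the assumed UKA, obese and loser shares. Say that the medial UKA strata are reported for precision only.

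Optionally, add one all-BMI row per procedure to Table 2, adjusted for obesity status, age, sex and cement. This would give an estimate for THA close to the planned one. It would not restore the planned knee population, because TKA and medial UKA stay separate.

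The cost is a reworded paragraph and, if the option is taken, three table rows; no more patients are needed. The downside is that the stated detectable differences become less favourable than the present calculation implies.

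### The 16.6% detectable difference has no scale or reference incidence: it is about twice any absolute difference the inputs allow, and as a relative difference it holds only near 50% incidence

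*Combined protocol and SAP*

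**What the plan says.** All the inputs are in Methods, Statistical analysis.

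- Sample: "We expect to find a sample of around 6400 patients divided between hip and knee arthroplasty".
- Analysed number: "Estimated response rates of 70% will leave us with 2240 patients to be analysed in each joint arthroplasty group".
- Exposure split: "With an expected 15% of the sample to be weight gainers".
- Claim: "we will be able to detect a minimum of 16.6% difference in the incidence of the outcome between gainers and non-gainers", at a significance level of 0.05 and power of 0.80.

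The same section defines PPP as a pain score above 3 on the numerical rating scale but gives no expected incidence in any weight group. It names no formula or software for the power calculation and does not say whether the test is one- or two-sided.

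The planned analysis is set out in finer terms than the power statement. "We will report results for THA, TKA and medial UKA separately", odds ratios are to be estimated "amongst gainers and losers in relation to those who maintained their weight", and "We will stratify for baseline obesity status". Table 2 accordingly has six rows: total hip arthroplasty (THA), total knee arthroplasty (TKA) and medial unicompartmental knee arthroplasty (UKA), each split into non-obese and obese.

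**The concern.** For a binary outcome, the detectable difference depends on the reference incidence. A single percentage without that incidence, and without a scale, cannot be checked or interpreted. The plain sense of a difference in incidence is absolute, and 16.6 points looks far too large for 336 against 1904 patients at 80% power. The other common sense, a relative difference, looks far too small unless PPP is very common.

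This is the plan's only power statement, and its error changes direction with the reading. If absolute, it understates the study's sensitivity about two-fold. If relative, with incidence well below 50%, it overstates sensitivity. A reader weighing a null result could not tell which applies. The sentence does not determine how many patients are surveyed, so what is at stake is a misleading statement of power, not a wrong sample size.

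**Working it through.** **Inputs.** From the plan: 6400 patients, 70% response, 15% gainers, alpha 0.05, power 0.80. The equal hip/knee split is implied by the stated 2240. Reference incidences are my assumptions, because the documents give none.

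**Group sizes.** 6400 / 2 × 0.70 = 2240, as stated. Gainers: 0.15 × 2240 = 336. Non-gainers: 2240 − 336 = 1904.

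**Reproducing 16.6.** The arcsine effect size needs no reference incidence:

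h = (z₀.₉₇₅ + z₀.₈₀) × √(1/336 + 1/1904) = (1.960 + 0.842) × 0.05917 = 0.1658.

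This rounds to 0.166. The one-sided version gives 0.147, so the match is to a two-sided test. Here h = 2·arcsin√p₁ − 2·arcsin√p₀, a difference between transformed proportions. It is not a percentage-point or relative difference in incidence.

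**Absolute reading.** I used the pooled-variance two-proportion z-test:

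power = Φ((|p₁ − p₀| − 1.960·SE₀) / SE₁), where SE₀ = √[p̄(1 − p̄)(1/336 + 1/1904)], SE₁ = √[p₁(1 − p₁)/336 + p₀(1 − p₀)/1904], and p̄ is the pooled incidence.

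Example at p₀ = 0.20, p₁ = 0.269: p̄ = 0.2104, SE₀ = 0.02412, SE₁ = 0.02587, and power = Φ((0.069 − 0.04727) / 0.02587) = 0.80.

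Solving for 80% power:

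| Assumed incidence in non-gainers | Detectable increase (points) | Relative increase | Odds ratio |
|---|---|---|---|
| 10% | 5.4 | 54% | 1.63 |
| 20% | 6.9 | 35% | 1.47 |
| 30% | 7.8 | 26% | 1.42 |
| 50% | 8.3 | 16.5% | 1.40 |

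The maximum over all reference incidences is 8.27 points, at about 47%; for decreases it is also 8.27, at about 53%. With a continuity correction the maximum is 8.45, and one-sided it is 7.34. No variant approaches 16.6. The stated figure is 16.6 / 8.27 = 2.0 times the maximum and 16.6 / 6.9 = 2.4 times the value at 20%. Power for a 16.6-point difference is lowest, at 99.99%, for an increase from 40%.

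**Relative reading.** Set p₁ = 1.166 × p₀. At p₀ = 0.20 this is 20% vs 23.3%: SE₀ = 0.02389, SE₁ = 0.02482, and power = Φ((0.0332 − 0.04682) / 0.02482) = 0.29.

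| Assumed incidence in non-gainers | Power for a 16.6% relative increase |
|---|---|
| 10% | 16% |
| 20% | 29% |
| 30% | 45% |
| 50% | 80% |

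Power reaches 80% at an incidence of 49.8% (44.2% if one-sided). The agreement near 50% follows from the arcsine scale: there the absolute difference is about h/2, so the relative difference is about h.

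**Simulation check** at 20% (200,000 draws): power 0.799 for 20% vs 26.9%, 0.292 for 20% vs 23.3%, and above 0.9999 for 20% vs 36.6%.

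**Comparator.** The plan tests gainers against maintainers, not all non-gainers. For a whole joint group at 20%, with assumed loser shares of 5% to 20%, the detectable increase is 6.9 to 7.1 points, so the comparator alone changes little. Losers against maintainers depends on the loser share, which the plan does not give: 11.5, 8.3, 7.0 and 6.3 points for assumed shares of 5%, 10%, 15% and 20%.

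**The case against.** The strongest defence is that the calculation was probably right. The plan's own inputs give 0.166 exactly as a two-sided effect size, so the fault would be one of labelling. I accept that as the likely explanation, although it is an inference. It does not rescue the sentence, because the quantity printed is called a difference in incidence, and h = 0.166 corresponds to about 5 to 8 points at incidences of 10% to 50%.

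Second, two-sidedness can reasonably be inferred from the planned 95% confidence intervals and from the effect-size match. That is fair. Scale and reference incidence are the omissions that matter, and stating sidedness only completes the sentence.

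Third, the sample is fixed by the registers and the response rate, precision will be judged from the confidence intervals, and on the absolute reading the error is conservative. All of this stands and limits the consequence. It does not make the plan's only power figure correct, and the conservative direction holds on one reading only.

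Fourth, with a continuity correction the overstatement of the detectable difference is 16.6 / 8.45 = 1.96, so about two-fold is the accurate phrase.

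**Conclusion.** The concern holds and should be fixed. As an absolute difference the stated figure is wrong whatever the PPP incidence: the two-sided maximum is 8.3 points, half of 16.6. This conclusion needs no assumed incidence, only the plan's inputs and a standard two-proportion test. As a relative difference it is right only if about half of non-gainers have PPP (about 44% if one-sided), which the plan neither states nor supports. The values at 10%, 20% and 30% rest on assumed incidences and show the range. The arcsine origin is likely but unconfirmed, and the verdict does not depend on it.

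**What to change.** Replace the sentence with one that states the expected PPP incidence in the reference group, a two-sided test, and the resulting absolute difference or odds ratio. For example:

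> Across a whole joint group (336 gainers, 1904 non-gainers), assuming PPP in 20% of non-gainers, we have 80% power at two-sided alpha 0.05 to detect 20% vs 26.9% (odds ratio about 1.47). For reference incidences of 10% to 30% the detectable increase is 5.4 to 7.8 percentage points.

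The 20% is a placeholder; the sponsor should substitute its own expected incidence and recompute. If a relative difference at 50% incidence was intended, say so and justify the 50%.

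Add one sentence on scope: the figure applies to a whole joint group and not to the Table 2 rows. For gainers against maintainers, each row has fewer gainers and fewer reference patients, so at the same incidence the detectable difference is larger. For losers against maintainers it also depends on the loser share. If detectable differences are reported for the rows, they should use the sponsor's own expected numbers of gainers, losers and maintainers and cover both contrasts.

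The cost is two sentences in the Statistical analysis section, with no change to design, sample size or analysis.

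### PPP odds ratios are planned only within obesity strata; an overall odds ratio per procedure and an interaction test should be added, keeping the stratum rows

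*Combined protocol and SAP*

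**What the plan says.** The objective, at the end of the Introduction, is to find out "whether weight change is associated with the incidence of PPP following THA and knee arthroplasty across non-obese and obese patients".

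Under Statistical analysis the sample is sized at joint level: "We expect to find a sample of around 6400 patients divided between hip and knee arthroplasty", and "Estimated response rates of 70% will leave us with 2240 patients to be analysed in each joint arthroplasty group". The stated detectable effect is "a minimum of 16.6% difference in the incidence of the outcome between gainers and non-gainers", at alpha 0.05 and 80% power.

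The same section then separates the three procedures ("We will report results for THA, TKA and medial UKA separately"), on the ground that the authors regard them as distinct patient populations. It describes a logistic model comparing gainers and losers with those who kept their weight, and adds "We will stratify for baseline obesity status", with the cut at a BMI of 30. The adjusters are age, sex and cement; obesity enters only through stratification.

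In the Table 2 shell the reference OR of 1 is printed in the non-obese and obese rows. The THA, TKA and medial UKA lines carry no reference value and read as headings. No overall OR per procedure is specified, and neither is a test of whether the association differs between non-obese and obese patients.

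**The concern.** The primary outcome will be reported as 12 adjusted ORs (3 procedures x 2 obesity strata x 2 contrasts). Each procedure's data are split by obesity and, as far as the plan states, not recombined. If weight change has much the same association with PPP in both strata, the estimate that uses all the data for that shared association is missing.

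Two consequences follow. A real association can miss significance in one or both rows although the procedure as a whole would show it. And when one row is significant and the other is not, the plan offers nothing to stop that pattern being read as a difference by obesity.

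The level at which the study is sized also does not appear in the results. For THA the joint group and the procedure are the same 2240 patients, and Table 2 has no estimate on them.

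**Working it through.** **1. The plan's own figures.** Analysed per joint group: 6400 x 0.70 / 2 = 2240, as stated. With 15% gainers, that is 336 gainers and 1904 non-gainers. The detectable standardised effect (Cohen's h) at two-sided 0.05 and 80% power is (1.960 + 0.842) x sqrt(1/336 + 1/1904) = 0.166. The stated 16.6% therefore reproduces as a standardised effect on the whole joint group. It does not reproduce as a difference in percentage points, which would be about 5.4, 6.9 and 7.8 points at non-gainer rates of 10%, 20% and 30%. That labelling is a separate matter. What counts here is that the calculation uses the undivided 2240.

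**2. Inputs for the comparison (THA, gainers v maintained).**
- From the plan: N = 2240; 15% gainers; alpha 0.05.
- Assumed, because the documents give no figure: 15% losers (so 70% maintained); PPP in maintainers 20%, range 10-30%; obese share 25-45%; the same gainer share and PPP rate in both strata; true OR 1.5 in both strata.

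**3. Overall estimate.** PPP in gainers at OR 1.5: odds 1.5 x 0.20/0.80 = 0.375, so 0.375/1.375 = 0.273.

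SE(log OR) = sqrt[1/(n1 p1 q1) + 1/(n0 p0 q0)], with n1 = 336 and n0 = 0.70 x 2240 = 1568:

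sqrt[1/(336 x 0.273 x 0.727) + 1/(1568 x 0.20 x 0.80)] = sqrt(0.01500 + 0.00399) = 0.138.

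Power = Phi(ln 1.5 / SE - 1.96) = Phi(0.405/0.138 - 1.96) = 84%.

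**4. Stratum rows.** Under these assumptions the SE in a row is the overall SE divided by the square root of the stratum's share.

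| Obese share | SE non-obese | Power | SE obese | Power | Both rows significant | Neither |
|---|---|---|---|---|---|---|
| 25% | 0.138/sqrt(0.75) = 0.159 | 72% | 0.138/sqrt(0.25) = 0.276 | 31% | 23% | 19% |
| 45% | 0.138/sqrt(0.55) = 0.186 | 59% | 0.138/sqrt(0.45) = 0.205 | 51% | 30% | 20% |

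The last two columns are products of independent probabilities, for example 0.72 x 0.31 = 0.23. The remainder, 50-58%, is exactly one row significant although the true OR is identical in both. On the log scale the row intervals are about 15-35% wider (non-obese) and 50-100% wider (obese) than the overall interval.

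**5. Range over PPP of 10-30%.**

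| PPP in maintainers | Overall | Non-obese row | Obese row |
|---|---|---|---|
| 10% | 63% | 40-51% | 21-34% |
| 20% | 84% | 59-72% | 31-51% |
| 30% | 90% | 67-80% | 37-59% |

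**6. TKA.** If TKA were 80% of the knee group (assumed), N = 1792. At PPP 20% the power is 75% overall, 50-63% non-obese and 26-42% obese. Medial UKA, as the smaller remainder under that assumption, would be weaker still.

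**7. What an interaction test can show.** For THA at PPP 20%, the SE of the difference between the two log ORs is sqrt(0.159^2 + 0.276^2) = 0.318 at 25% obese and sqrt(0.186^2 + 0.205^2) = 0.277 at 45%. The ratio of ORs detectable at 80% power is exp(2.80 x 0.277) = 2.2 to exp(2.80 x 0.318) = 2.4.

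**The case against.** The strongest reply is that the objective itself asks about the association across non-obese and obese patients, so obesity-specific ORs answer it directly. A further planned sensitivity analysis compares effect size between morbid and non-morbid obesity, which fits that reading. This stands: the stratum rows are legitimate, and an overall OR should not displace them or be named as the only answer.

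A reader might infer that every reported row is less precise than the data allow. The documents do not support that. A row already uses all patients in its stratum; an overall OR estimates a different quantity and does not sharpen any row. The gain is for a shared association, and only if the ORs are similar.

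A reader might also infer that the study question is left without a single answer and that an overall OR would supply one. It would not: three procedures and two contrasts still give six overall ORs.

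Two further points stand in part. No sentence rules out an overall model; its absence is read from the Table 2 shell and the silence of the text. And a reader of the finished table could pool the strata from the printed counts or ORs, so no information is lost. But an estimate assembled afterwards by readers is not a pre-specified one, and if the authors do intend it, the plan should say so.

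Separate reporting by procedure is reasoned in the plan and is not at issue.

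**Conclusion.** The point holds as a low-cost improvement, not as an error that invalidates the planned analysis. The plan specifies PPP odds ratios only within obesity strata, sizes the study on an undivided joint group, and gives no test for a difference between strata.

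If the association is similar in both strata, the overall THA estimate has markedly higher power than either row, across the whole range of PPP rates examined. About half of studies or slightly more would show one significant row and one non-significant row with no true difference behind it (THA, PPP 20%).

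These sizes rest on assumed PPP rates, obese and loser shares, equal gainer shares and PPP rates across strata, and a true OR of 1.5; none of these is in the documents. The ratio of row SE to overall SE depends only on the obese share once PPP rates, gainer shares and the OR are taken as equal. If the association truly differs by obesity, the power comparison no longer applies and the stratum rows carry the message.

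**What to change.** Keep THA, TKA and medial UKA separate, and keep the non-obese and obese rows. Then:

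1. For each procedure, fit one model with weight-change group plus baseline obesity status, and a second that also includes age, sex and cement. Report the ORs and 95% CIs (gainers v maintained, losers v maintained) in the THA, TKA and medial UKA rows of Table 2.
2. For each procedure, add a weight-change-by-obesity interaction test. State that a difference between strata will not be inferred from one row being significant and the other not.
3. State how the overall and stratum ORs will be read together, without making the overall OR the sole answer to the objective.

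The cost is a few extra models per procedure, three filled table rows and one reported test per procedure, all from variables already collected. The downside is that the overall OR averages over any true difference by obesity; the stratum rows and the interaction test are there to show it. The test detects only large differences (a ratio of ORs of about 2.2-2.4 for THA under the assumptions above), so a non-significant result should not be reported as proof that the strata agree.
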